### Analysis of pilot trial store impact data (Aim 3)

We hypothesize that there will be significantly increased availability (stocking) and sales of healthy promoted foods (whole grain, fruit, vegetable, and low-fat, low-sugar foods) and beverages in intervention stores using the BUD app, as compared to comparison stores. Using direct observation-based stocking data, a healthy food availability index (HFAI) will be calculated, and we will initially examine the difference from pre- to

postintervention comparing intervention and control stores. We will also look at change in availability and sales of specific promoted product categories from pre- to post-intervention at each specific phase of intervention. Mixed-effect models, treating the stores as a random effect, will be used to evaluate the effect of the intervention on availability/sales of healthful food and beverage scores comparing corner store intervention and comparison groups, adjusting for covariates, such as store size and food stocking at baseline. We hypothesize that prices of some promoted foods and beverages will decrease given promoted foods/beverages will be subsidized during the first two phases of the intervention, as compared to baseline (if stocked at baseline). Furthermore, we will conduct additional tests to see if a pass-through price effect occurred related to the initial subsidy. Since the subsidy is short term (just phases 1 and 2 of the intervention), relatively small, and intended to generate initial usage of the app, we do not anticipate a significant price effect.

#### Analysis of pilot trial consumer impact data (Aim 4)

Secondary outcome analyses will include assessment of change in consumer-level variables. From the adult consumer impact questionnaire (AIQ) on purchasing frequency of promoted foods and beverages (i.e. fruit and vegetables, low-fat snacks, low-sugar beverages, whole grain foods), and using the Block FFQ data on the intake of the same products, we will compare the change in purchasing and consumption among consumers of intervention stores to the comparison store consumers. These analyses will be adjusted for potential confounders, such as age, sex, income, participation in food assistance programs, and other household covariates when appropriate. We will use linear mixed-effect models with individual and store random effects to identify potential predictors of participation. We hypothesize there will be a trend toward increased purchasing and consumption of healthy promoted foods and beverages among intervention consumers compared to consumers that are sampled from comparison stores.

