C.8.4. Consumer-level instruments: The Adult Impact Questionnaire (AIQ) will be a modified version of a survey that we have used in previous studies. This instrument will collect sociodemographic information and food purchasing behavior such as how many times a product was bought and from which type of store (i.e., corner store, grocery store, urban farm, etc.). In particular, we will assess purchasing of promoted products from participating corner stores. Body weight to the nearest 0.1 kg and body composition (% body fat and lean mass) will be measured with Bioimpedance Analysis (BIA) using the Tanita-BIA (Model BF679W). Height to the nearest 1 mm will be measured with a stadiometer (Seca 213). Waist and hip circumference will be measured to the nearest 0.1 cm with a measuring tape. Three measures will be made, and the closest two measures averaged. The AIQ will be performed at baseline and post-intervention (2 times). The Adult Block Food Frequency Questionnaire (FFQ) will estimate adult consumer food intake and nutrient consumption (e.g., total energy intake, total fat, added sugar, sugar sweetened beverage and fruit and vegetable intake). Several studies have validated this instrument. Completed FFQs will be analyzed by NutritionQuest (Berkeley, California) and estimates of food patterns and nutrient intakes will be generated. The FFQ will be performed at baseline and post-intervention (2 times). *All consumer measures will take place at the Johns Hopkins Bloomberg School of Public Health in a private office.*

C.8.5. Process evaluation instruments: Process evaluation instruments will be developed to measure the reach, dose delivered, and fidelity of the BUD intervention implementation. The team will develop specific standards for each process evaluation component that will be measured through multiple interventionist data collection forms, as well as through the BUD app itself. We will incorporate both quantitative and qualitative open-ended questions which will permit us to assess user experiences with the BUD app in terms of satisfaction, including challenges and potential solutions. All instruments will be electronic forms developed using REDCap, as we have used for our ongoing multicomponent intervention trial. See Outcome Measures and Statistical Design Plan for more details.

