## Statistical Design Plan

The data analysis plan is a series of steps including data entry, data cleaning, exploratory data analysis, and multivariate analysis, led by our biostatistician ([name]) and by our economist ([name]) for the economic analysis. Data will be managed at JHU and the data manager will review data for quality. Qualitative data will be de-identified, transcribed and translated (if needed) by research assistants, kept on password protected computers, and analyzed using Atlas-ti 8.4. Quantitative data will be de-identified, entered into Microsoft Access databases and analyzed using Stata 14. These data will be collected through direct observation (e.g., availability), electronic point of sale data collection (e.g., sales), surveys (e.g., consumer purchasing), and anthropometry (e.g., BMI). We will look at the change in availability, sales, and purchasing of healthier foods scores from baseline to post-intervention comparing intervention and comparison groups, at the store and consumer levels. Models will control for covariates that predict the outcomes (e.g., store size or consumer age and sex), and standard errors will account for the clustering of repeated measures within stores.

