Sample size calculations for corner stores were based on the analysis of a simple difference in change in the mean of Healthy Food Availability Index (HFAI) scores. We used preliminary impact data from our previous trial (BHCK), with a reported mean change in HFAI  $\mu(\sigma) = 1.67(5.35)$  and  $\mu(\sigma) = 5.65(4.95)$  in the control and intervention groups, respectively. Due to the price incentive features (subsidy, group purchasing discounts) that will be available to BUD stores owners to stock healthier foods and beverages in phases 1 and 2, we estimate that the effect of the BUD intervention will be higher than our previous studies with corner stores. Therefore, we estimated a total sample size of 34 stores (17 per arm) for two-sample comparison of mean assuming a difference in healthy food availability (HFAI) of 6 points, variance of 24, intraclass correlation of 0.0001, type I error of 5% and power level set at 80%. We will increase our store sample size by 2 per treatment arm (n=38) to account for possible loss to follow-up. As mentioned, we will also control for baseline covariance, which will help to increase the power of the study. Some of the potential factors to control for will include store size and baseline HFAI.

The consumer sample size of this feasibility trial is intended to obtain an estimate of effect size and the variance in food consumption, purchasing, and body mass index, in order to plan a larger clinical trial, and to provide evidence of recruitment and retention ability. Therefore, the R34 pilot study is not powered to provide impact at the consumer level (which will be the primary outcomes for the full-scale clinical trial). Consumer eligibility criteria are as follows: 1) frequent consumer of the food store (shop at least once a week); 2) live/work within 1/4 mile radius from the store; 3) >21 years old and < 75 years old; 4) live in a household of at least 2 persons. We will use systematic sampling to recruit the consumer study evaluation sample in and around each of the 38 small food stores (5 adult consumers per food store).

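### Aim 4 compares change in consumer purchasing and intake and does not name the consumer's own baseline value as a covariate, which gives up precision for no saving

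*Combined protocol and SAP*

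**What the plan says.** In the Statistical Design Plan, under Analysis of pilot trial consumer impact data (Aim 4), the comparison is one of change: "we will compare the change in purchasing and consumption among consumers of intervention stores to the comparison store consumers". On covariates it says: "These analyses will be adjusted for potential confounders, such as age, sex, income, participation in food assistance programs, and other household covariates when appropriate". The same paragraph names a mixed model, but for another purpose: "We will use linear mixed-effect models with individual and store random effects to identify potential predictors of participation".

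The opening paragraph of the Statistical Design Plan gives a general rule: "Models will control for covariates that predict the outcomes (e.g., store size or consumer age and sex". Age and sex are the only consumer examples.

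For stores, baseline values are named. The Aim 3 model is described as "adjusting for covariates, such as store size and food stocking at baseline", and Power Calculation and Study Design adds: "Some of the potential factors to control for will include store size and baseline HFAI". That section also says that this kind of control should raise power.

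Section C.8.4 schedules the Adult Impact Questionnaire (AIQ, purchasing) and the food frequency questionnaire (FFQ, intake) twice each, at baseline and after the intervention. Section C.1 puts baseline collection in months 10-12 and randomization in the phase that starts in month 13.

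**The concern.** A change score fixes the coefficient on the baseline value at 1. When the two visits have equal variance, the slope that the data support is r, which is below 1. The change score therefore subtracts too much of the baseline. This adds noise, and it lets a chance difference between arms at baseline carry into the estimated effect with the opposite sign. Adjusting for age, sex, income and food assistance does not remove this, because a consumer's earlier purchasing or intake is usually the strongest single predictor of the later value.

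What is at stake is the precision of the consumer estimates. Power Calculation and Study Design says that the consumer sample exists to estimate effect size and variability for a larger trial, in which consumer outcomes will be primary. The section on using the data to power the main trial says that the pilot is meant to estimate that trial's primary outcomes with adequate precision. A wider interval than the data require works against that purpose.

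**Working it through.** **The plan's own figures.** The documents give no power or precision figure for the consumer analysis. The one sample-size calculation concerns the store availability index (HFAI) and does not bear on this point. The consumer number follows from the design: 38 stores × 5 consumers = 190, or 95 per arm.

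**Inputs.**
- Two measurements per consumer (C.8.4), the first before randomization (C.1).
- r, the within-consumer pre-post correlation left after the listed covariates. It is not in the documents; the pilot itself plans to estimate within-participant correlation over time. Assumed range: 0.3 to 0.8.
- Equal outcome variance s² at the two visits (assumed).

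**Formulas**, for the per-consumer variance that enters the arm difference:
- change score: 2s²(1 − r)
- baseline-adjusted: s²(1 − r²)
- ratio: (1 − r)(1 + r) / [2(1 − r)] = (1 + r)/2

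With 95 per arm and clustering and drop-out ignored, the 95% half-width in SD units is 1.96 × √(2/95) × √v = 0.284 × √v, where v is the variance above with s² = 1.

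| r | v, change | v, adjusted | Ratio | Fall in SE | Half-width, change | Half-width, adjusted |
|---|---|---|---|---|---|---|
| 0.3 | 1.40 | 0.91 | 0.65 | 19% | 0.34 | 0.27 |
| 0.5 | 1.00 | 0.75 | 0.75 | 13% | 0.28 | 0.25 |
| 0.7 | 0.60 | 0.51 | 0.85 | 8% | 0.22 | 0.20 |
| 0.8 | 0.40 | 0.36 | 0.90 | 5% | 0.18 | 0.17 |

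**Unequal variances.** With SDs s₀ at baseline and s₁ afterwards, the change-score variance minus the adjusted variance is (s₀² + s₁² − 2r s₀s₁) − s₁²(1 − r²) = (s₀ − r s₁)². This is never negative, so apart from the trivial cost of estimating one slope, baseline adjustment does not lose. The size of the gain does depend on the variances.

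**Clustering.** A simulation used 38 stores of 5 consumers, 19 stores per arm, and compared the change score with a regression on arm and the consumer's baseline. With a store intraclass correlation of 0.05 the variance ratios were 0.69, 0.75 and 0.84 at r = 0.3, 0.5 and 0.7. With no clustering they were 0.68, 0.76 and 0.85. With r = 0.5, an intraclass correlation of 0.05 and store effects correlated 0.9 over time, the ratio was 0.81. Clustering shifts the gain but does not remove it.

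**Chance imbalance.** If the arms differ by d at baseline, the change score is off by −(1 − r)d in that sample. Ignoring clustering, one standard error of d is √(2/95) = 0.145 SD. At r = 0.5 this moves the estimate by 0.5 × 0.145 = 0.07 SD. Over repeated randomizations the error averages to zero.

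**Does the planned mixed model already do this?** Only under a condition that the plan does not state. With two complete visits and baseline means free to differ by arm, a model with an individual random effect returns the change-score estimate. It gains the precision of baseline adjustment only if the baseline means are constrained equal.

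**The case against.** The best defence is that the plan does not rule baseline out. The Aim 4 list is introduced by examples, and the general rule admits any covariate that predicts the outcome, which a baseline value ordinarily would. This stands: baseline is unnamed, not excluded, and a reader who infers a commitment to omit it goes further than the text. But an open list leaves the most useful covariate to be chosen after the data are seen, and the stated comparison is still one of change.

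A second defence is the mixed model with individual and store random effects. The text ties it to participation, not to the arm effect, and does not constrain the baseline means, so it does not settle the matter.

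Third, Aim 4 is secondary, hypothesizes only a trend, and is expressly unpowered. The plan also estimates within-participant correlation, so the main trial could be sized for a baseline-adjusted analysis in any case. This stands and limits the importance of the point. What remains is a wider interval than necessary on the pilot's effect estimate.

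Three stronger readings are tempting and are not supported:
- That the effect estimate is biased. Stores are randomized after baseline, so the change score is unbiased on average.
- That Aim 3 sales share the gap because baseline sales are not named. Power Calculation and Study Design commits to controlling store baseline covariates that may predict outcomes, and the Aim 3 list is open too. The two-visit formula also does not fit sales recorded at the point of sale.
- That the variance ratio converts into a number of extra consumers. In a 38-store design, adding consumers within stores is not the same as adding stores.

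**Conclusion.** The point holds for Aim 4 alone. The stated analysis compares change, and the consumer's own baseline value is not named as a covariate although it is collected before randomization. Baseline adjustment would bring the variance of the arm effect to about 0.65 to 0.90 of the change-score variance. This assumes r between 0.3 and 0.8 after the listed covariates, equal variances at the two visits, and no clustering; clustering changes the figures modestly. The gain shrinks as r approaches 1. The loss is one of precision, with exposure to chance baseline imbalance, in a secondary and unpowered aim whose estimates will inform the main trial. It is a free improvement, not a flaw that invalidates the analysis.

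**What to change.** In the Aim 4 section, state the arm-effect model: the post-intervention value of each outcome regressed on arm, the same outcome's baseline value, the listed covariates and a store random effect. An equivalent choice is a mixed model of both visits with individual and store random effects and baseline means constrained equal across arms; this also keeps consumers who have only a baseline visit. Separate this from the sentence on predictors of participation. Change can still be reported descriptively.

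The cost is a few lines of text. No new data, visits or participants are needed.

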#### Economic analysis (Aim 5)

We will conduct a cost–benefit analysis of the use of the BUD App, from the wholesaler, producer, retailer and consumer perspectives. We hypothesize that the savings promoted by the BUD App will outweigh the costs of developing and implementing the intervention. In other words, we hypothesis that the use of the BUD App will have a high rate of return for the wholesaler as well as retailers and consumers.

Among the potential savings from using BUD, we will include: reduction in prices of foods; increase in total net revenues (sales minus discounts); reduction in transportation cost of food, reduction in transportation costs to buy products; inventory and rotation; financial costs of working capital among other items. Other benefits associated with the BUD are linked with improvement in health and human capital of consumers. We would consider these savings broadly using our sample of 170 low-income urban consumers, assessed pre- and post-intervention variation and will monetize benefits associated to these outcomes. We will separate between short-term and long-term benefits and discount future benefits.

For cost, we will include in our analyses monthly and annual totals, including costs at baseline, personnel costs (salaries and benefits), material and supplies, equipment, and transportation costs, among other items. We will also monetize the time of delivering the intervention and the time devoted to training. We plan to differentiate between initial costs and deployment costs. Initial costs will account all costs during the pre-implementation phase of the intervention. Post-intervention costs will capture the variable and fixed costs of running the program. These costs will include recurrent and capital costs associated to the program. We plan to integrate these templates to estimate the total costs of the intervention and compare these figures to the benefits of the program. We will conduct sensitivity analyses to test how robust our results are, in relation to the assumptions of our financial cost model.

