#### **B.5. We will examine the costs/benefits of using the BUD app in relation to sales in small food stores**

Led by our economist ([name]), we will conduct a financial cost–benefit analysis of the use of the BUD app from the wholesaler, producer and retailer perspectives. We will include in our analysis monthly, and annual totals, including costs at baseline, personnel costs (salaries and benefits), materials and supplies, equipment, and transportation costs, among other items. We will also monetize the time of delivering the intervention and the time devoted to training. We plan to differentiate between initial costs and deployment costs. Initial costs will account for all costs during the pre-implementation phase of the intervention. Post-intervention costs will capture the variable and fixed costs of running the program. We will integrate these templates to estimate the total costs of the intervention and compare these figures to the benefits of the program. Among the potential savings from using BUD, we will include: prices of foods; total net revenues (sales minus discounts); transportation cost of food, transportation costs to buy products; inventory and rotation; financial costs of working capital among other items. Other benefits associated with the BUD are linked with improvement in health and human capital. We would consider these savings broadly using our sample of 190 low-income urban consumers, assessed pre- and post-intervention variation and will monetize outcomes. **We will assess the economic viability of the BUD app, an essential component of feasibility.**

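### The cost-benefit analysis (Aim 5) credits added net revenue as a saving, and no named cost covers buying the extra goods sold

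*Combined protocol and SAP*

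**What the plan says.** Two places describe the analysis: protocol section B.5, and the Economic analysis (Aim 5) in the Statistical Design Plan.

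- **Benefits.** Aim 5 opens its list with "Among the potential savings from using BUD, we will include: reduction in prices of foods", then adds "increase in total net revenues (sales minus discounts", transport savings, and "inventory and rotation; financial costs of working capital among other items". B.5 lists "total net revenues (sales minus discounts" among the potential savings. In both places discounts are the only deduction.
- **Costs.** Aim 5 names "personnel costs (salaries and benefits), material and supplies, equipment, and transportation costs, among other items", plus time spent on delivery and training. On running costs it says: "Post-intervention costs will capture the variable and fixed costs of running the program".
- **Perspectives.** Aim 5 works "from the wholesaler, producer, retailer and consumer perspectives"; B.5 omits the consumer.
- **Hypothesis.** "We hypothesize that the savings promoted by the BUD App will outweigh the costs of developing and implementing the intervention". The next sentence restates this as a high return for the wholesaler, retailers and consumers.

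Cost of goods, gross margin and profit appear in neither account. Neither place says whether the perspectives are to be added together.

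**The concern.** A store that sells more fruit must first buy it, so its gain is the margin on those sales and not the takings. The plan defines the benefit as takings net of discounts. Its cost list concerns the program, not the stores' stock purchases. Aim 3 hypothesizes higher sales of promoted foods, so the gap matters most if the trial succeeds.

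Elsewhere the protocol treats profit as the relevant quantity: Stage 4 training (C.9) addresses profitability, and the feasibility analysis asks whether new products are seen as profitable. B.5 makes economic viability an essential part of feasibility, and A.4 expects the private sector to take up the app once benefits are shown. A return built on revenue would be a poor guide for a store or wholesaler deciding whether to adopt it.

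**Working it through.** The plan states no rate of return, benefit-cost ratio, margin or cost amount, so there is no figure to reproduce. The check is one of accounting.

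**Step 1. What the lists leave out for a retailer.** Let *p* be the selling price net of discounts, *c* the unit purchase price and *q* the units sold, with 0 for before and 1 for after.

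- Change in gross margin = (p1·q1 − p0·q0) − (c1·q1 − c0·q0).
- The change in the purchase bill splits as c1·q1 − c0·q0 = c1·(q1 − q0) − (c0 − c1)·q0.
- So change in gross margin = added net revenue + price saving on the old volume, (c0 − c1)·q0 − cost of the extra units, c1·(q1 − q0).

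The first two terms match items in the benefit list. The third is named in neither list. If the price saving is valued on the new volume instead, the missing term becomes c0·(q1 − q0). It is zero only if volume does not rise. The split also shows that gross margin already contains the retailer's lower purchase price.

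**Step 2. Size for the revenue item.** At unchanged prices and gross margin *m*, added net revenue *R* yields a gain of R·m. The overstatement factor is R/(R·m) = 1/m. The margins below are assumptions.

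| Assumed margin | Credited | Gain after cost of goods | Factor |
|---|---|---|---|
| 20% | $100 | $20 | 5.0 |
| 30% | $100 | $30 | 3.3 |
| 40% | $100 | $40 | 2.5 |

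**Step 3. Effect on the overall return.** If revenue makes up a share *s* of all credited benefit, corrected benefit divided by credited benefit = (1 − s) + s·m. This runs from 1 at s = 0 to m at s = 1. The documents give neither s nor m. In the limiting case s = 1, an apparent benefit-cost ratio of 2.0 (hypothetical) becomes 2.0 × 0.2 = 0.4, 2.0 × 0.3 = 0.6 or 2.0 × 0.4 = 0.8. That is a bound, not an estimate.

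**Step 4. If perspectives were added.** The plan does not say that they will be.

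- *Price cut.* For a cut of 10% on $100 of sales at fixed volume, the buyer gains $10 and the seller's net revenue falls by $10, because discounts are deducted. The sum is zero when both sides are entered.
- *Wholesale plus retail revenue on the same goods.* Take a retail value of $100. At assumed margins of 20% (retail) and 10% (wholesale), revenue is $100 + $80 = $180 against a combined margin of $20 + $8 = $28, a factor of 6.4. At 40% and 20%, revenue is $100 + $60 = $160 against $40 + $12 = $52, a factor of 3.1.
- *BUD Credit (C.9).* 19 stores × 2 stages × $100 = $3,800 if fully used, a transfer from the study to the stores.

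**The case against.** **The lists are open and nothing has been reported.** Both the benefit and the cost list end by allowing further items. Costs at baseline are listed without definition, inventory and working capital are named, and the costing templates and their cited source cannot be seen. Cost of goods might yet be included. This stands to the extent that nobody can say the return *is* overstated. It does not remove the point: the revenue definition is explicit, and cost of goods is its main missing deduction. The planned sensitivity analyses address the assumptions of the cost model, not this definition.

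**A reader might infer that counting lower food prices is itself an overstatement, since the buyer's gain is the seller's loss.** The documents do not support that. The analysis names separate perspectives, the hypothesis is restated by party, and in the buyer's own account a lower price is a genuine gain. Net revenue after discounts already enters the concession in the seller's account. Sections A.5 and A.6 also expect savings from cheaper last-mile and shared delivery and from less uncertain demand, which are not transfers. A price cut would be overcounted only if perspectives were added with one side left out, and the text does not say so.

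**The size is assumed.** This is correct. The factor rests on assumed margins and applies to one benefit item, for revenue from extra volume.

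**The stakes are modest.** This is a pilot whose store sample is sized on the Healthy Food Availability Index, and no go/no-go rule depends on a rate of return. That limits the consequence, but viability is still a declared component of feasibility.

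**Conclusion.** The point holds for the revenue item. As defined, added net revenue is credited as a saving while no named cost covers buying the added goods. Applied literally, that item would be overstated by 1/gross margin: 2.5 to 5 times at an assumed margin of 40% to 20%. The direction depends only on volume rising and goods having a purchase cost; the size depends on margins that the documents do not give.

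Two stronger conclusions do not follow. The overall return cannot be called overstated, because none is reported and the share of revenue in total benefit is unknown. The price-reduction item is not an error in itself. What is missing there is a rule for any combined figure.

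**What to change.** - **Retailers.** In Aim 5 and B.5, replace the revenue item with the change in gross margin: sales minus discounts minus cost of goods. Use the recorded unit sales and store prices (C.8.3) and the prices paid in the app log (C.8.6). Approximate purchases at baseline, outside the app and in comparison stores from wholesaler selling prices in the Wholesaler Impact Questionnaire (C.8.1). Pricing is listed there under app usage, so confirm that it is also asked at baseline. Do not add the retailer's lower purchase price as a further saving.
- **Wholesalers and producers.** No described instrument names their own cost of goods. Either add a cost question to the existing wholesaler and producer questionnaires, or report their revenue as revenue and not as a saving or net benefit.
- **Perspectives.** Report each one separately. If a combined figure is produced, enter both sides of every price cut and of BUD Credit, and do not add wholesale and retail revenue on the same goods.

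**Cost.** For retailers this is a wording change and modest extra analysis on data already planned. Wholesaler or producer margins need an added question, so some new data collection. The return will look less favourable, and purchase costs outside the app will be approximate; vary them in the sensitivity analyses.
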